10. STATISTICAL CONSIDERATIONS

10.1 Study design

Prospective, multicenter, phase II clinical trial designed for the evaluation of predictive tumor biomarkers in patients with advanced and / or metastatic colorectal cancer and non-mutated KRAS tumor treated with biweekly cetuximab as first-line treatment.

The main objective of this study is the validation of the biomarkers BRAF, IGF1P / MMp7 (DP) and PI3K-PTEN to predict PFS in patients with advanced and / or metastatic colorectal cancer with non-mutated KRAS treated with standard chemotherapy plus biweekly cetuximab as first line therapy.

The primary endpoint and secondary efficacy endpoint analysis will be based on the revised RECIST 1.1 criteria (Appendix E) for the intention-to-treat analysis group.

10.2. Study variables, subgroups and covariates

10.2.1 Principal endpoint

The primary endpoint is progression-free survival comparing two cohorts, which will be defined according to the classification based on the predictive ability of biomarkers to respond.

Progression-free survival time (PFS): time from the date of inclusion to the date of radiological progression or death (whichever occurs first). Subjects who have not exhibited progression while in the study and have not died while in the study will be censored on the last radiological evaluation date with no evidence of progression. Subjects who have completed study treatment before 48 weeks for any reason should be followed up every 12 weeks as described in this protocol. Subjects who have undergone surgery for metastases will not be censored on the date of surgery, but will be followed as described in the study every 12 weeks until progression is documented. Subjects receiving second-line treatment without documented disease progression will be censored on the date of the last radiological evaluation without progression prior to the change in treatment. If for any reason only the baseline CT was performed (resignation of the subject to continue in the study or loss of follow-up), the case will be censored on day +1 of the inclusion date.

10.2.2 Secondary endpoints

Objective response rate (ORR): incidence of a CR or PR according to the revised RECIST 1.1 criteria.

Duration of response (RD): (calculated only for subjects having an objective response) time from first objective response to progression of radiological disease according to the revised RECIST 1.1 criteria. For subjects who present a response and have not had progression, the duration of the response will be censored on the last assessment date of the evaluable disease.

Overall survival (OS): Time elapsed from the date of inclusion to the date of death. For subjects who have not died or who have been lost to follow-up by the data analysis cut-off date, the SG will be censored on the date of the last contact.

Safety: Type, frequency, intensity of adverse events related to the combination treatment.

10.2.3 Subgroup analysis

The intention-to-treat (ITT) analysis group is defined as all subjects who signed the informed consent and who have received the trial treatment, regardless of whether they actually receive any dose of the study treatment. Efficacy presentations will be made to the ITT review group.

A secondary analysis group (analysis group per protocol) will be used to evaluate the efficacy variables in all subjects who signed the informed consent and were included in the study and who did not present significant deviations from the protocol.

10.2.4 Covariates

Efficacy variables can be explored within the following subgroups:

Sex

Age

ECOG performance status

Location of the primary tumor (colon versus rectum)

Number of sites of metastatic disease (1 vs > 1 affected organ)

Baseline LDH concentration

Previous adjuvant chemotherapy (yes or no)

The rest of the subgroup analyzes that are carried out later, if they are carried out, must be notified as such, and the clinical report of the study must state the reason for said analyzes.

10.2.5 Considerations about the sample size

Two groups will be defined based on the classification constructed from the clinical variables and the proposed biomarkers.

The Log-rank method has been used instead of a binomial method for the sample calculation in order to include all the events that occur during follow-up.

A minimum difference of 20% (60 vs. 40%) in PFS is expected at 12 months between groups and with the following assumptions:

Alpha error (bilateral): 5%

Beta error: 20%

Monthly recruitment: 8 patients

Percentage of patients with classification = 0 is 40%

The number of patients required is 155 patients to be recruited in 24 months and a total duration of the trial (recruitment + follow-up) of 28 months for 115 events to occur.

Assuming 10% non-evaluable pts we should include a total of 170 pts.

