5.4 Estimated study duration

5.4.1 Study duration for the participants

The inclusion period is expected to last approximately 24 months.

Throughout the trial, subjects will be assessed for tumor response using Response Assessment Criteria for Solid Tumors (RECIST 1.1). The tumor response of the subjects will be evaluated by CT (helical or conventional) thoracic and abdominal performed in the baseline phase and every 12 weeks (three months) until the progression of the disease. In subjects with symptoms that indicate disease progression, tumor response should be assessed at the time of symptoms.

To assess overall survival, all patients will be followed up by visits to the center or by telephone contact every 12 weeks \pm 4 weeks from the date of progression up to 24 months after inclusion or death of the last subject, which happen first.

Therefore, the estimated maximum duration of the study is about 48 months (4 years).

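### Protocol 10.2.5: 60% vs 40% PFS with 155 patients gives about 85-101 events by month 28, not 115; the printed figures fit the SAP's 50% vs 30%, whose hazard ratio is misprinted

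*Protocol*

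**What the plan says.** Protocol 10.2.5 sizes the trial on a comparison of PFS between two classification groups. The method is stated: "The Log-rank method has been used instead of a binomial method for the sample calculation". The effect is stated: "A minimum difference of 20% (60 vs. 40%) in PFS is expected at 12 months between groups". The other inputs are a two-sided 5% alpha, 20% beta, "Monthly recruitment: 8 patients", and 40% of patients in class 0. The section does not say whether class 0 is the better or the worse group.

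The result is 155 patients recruited in 24 months, with "a total duration of the trial (recruitment + follow-up) of 28 months for 115 events to occur". An allowance for non-evaluable patients takes enrolment to 170. The Protocol synopsis repeats 60/40, 155 and 170.

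The SAP (synopsis and 6.5.2) keeps 155 patients and 115 events but gives the 12-month difference as 50% against 30%. SAP 6.5.2 says this corresponds to a hazard ratio of 1.79 under an exponential distribution. The SAP synopsis also repeats the 28 months.

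**The concern.** Three figures in Protocol 10.2.5 (the effect, the number of patients and the duration) together fix the expected number of events. A group with 60% PFS at 12 months progresses slowly, and patients recruited late in a 24-month window have only a few months of follow-up by month 28. An event yield of 115/155, or 74%, looks too high for that.

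At stake is whether the printed effect size is the one behind the printed design. Power in a log-rank comparison depends on events. The 115 also mattered later: the SAP uses it as the target that justified raising enrolment above 170. If the Protocol and SAP start from different effects and share one hazard ratio, a reader cannot tell what the 115 events were meant to detect.

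**Working it through.** **Inputs.** From Protocol 10.2.5: N = 155, T = 28 months, 12-month PFS 60/40, a 40:60 split, two-sided alpha 5%, 80% power, and accrual of either 24 months or 8 a month. From the SAP: 12-month PFS 50/30. Assumptions: exponential PFS (stated only in SAP 6.5.2), uniform accrual over A months, no dropout. Dropout would only lower the counts.

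**Hazard ratios.** For 60/40, ln 0.4 / ln 0.6 = 1.79. For 50/30, ln 0.3 / ln 0.5 = 1.74. The SAP's 1.79 is therefore the 60/40 value.

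**Accrual.** 155/8 = 19.4 months and 170/8 = 21.3 months. Filling 24 months needs 155/24 = 6.5 or 170/24 = 7.1 a month. Both A = 19.4 and A = 24 are carried through.

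**Events.** With λ = -ln(S12)/12, the chance of an event by T is

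p = 1 - [exp(-λ(T-A)) - exp(-λT)] / (λA).

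Expected events are 155 × [w·p(better) + (1-w)·p(worse)], where w is the share in the better group, 0.4 or 0.6.

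**Reproducing the printed figure.** Take 50/30, A = 19.4 and w = 0.4. Then p = 0.634 (better) and 0.814 (worse). Events are 62 × 0.634 + 93 × 0.814 = 39.3 + 75.7 = 115.1. Power, with variance 1/d1 + 1/d2 for the log hazard ratio, is 80.2%. That matches the stated 115 events, 28 months and 80%.

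**The Protocol's own 60/40.** With A = 19.4, p = 0.528 and 0.730; with A = 24, p = 0.472 and 0.662. For example, A = 24 and w = 0.4 gives 62 × 0.472 + 93 × 0.662 = 29.2 + 61.6 = 90.8.

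| Effect | Accrual (months) | Share in better group | Events at month 28 | Month of 115th event |
|---|---|---|---|---|
| 60/40 | 24 | 40% | 90.8 | 36.2 |
| 60/40 | 24 | 60% | 84.9 | 38.9 |
| 60/40 | 19.4 | 40% | 100.6 | 33.3 |
| 60/40 | 19.4 | 60% | 94.4 | 36.1 |
| 50/30 | 24 | 40% | 104.8 | 30.9 |
| 50/30 | 24 | 60% | 99.4 | 32.8 |
| 50/30 | 19.4 | 40% | 115.1 | 28.0 |
| 50/30 | 19.4 | 60% | 109.5 | 29.9 |

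The 60/40 shortfall at month 28 is 115 - 101 = 14 to 115 - 85 = 30 events, or 12-26% of the target. Changing the accrual assumption alone moves the count by about 10 events.

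**Power at month 28 under 60/40, N = 155.** Two formulas were used: the unequal-variance form above, and Schoenfeld with a 40:60 split, Φ(ln HR × √(0.24·d) - 1.96). With 24-month accrual they give 74-77% and 75-78%. At 8 a month they give 78-81% and 79-82%.

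**Sensitivity to N.** If all 170 enrolled patients were evaluable, 60/40 would give 93-106 events at month 28 (24-month accrual, or 21.3 months at 8 a month), still below 115.

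**The case against.** Several points on the other side carry weight.

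- **Month 28 is a forecast.** A reader might infer that the Protocol fixes an analysis at month 28 and so commits to an underpowered test. It does not. Section 10.2.5 gives 28 months as the expected time to 115 events and names no calendar trigger. Section 5.4.1 allows about 48 months in total, which leaves room for 33-39. The SAP treats 115 events as the target and reports 221 patients recruited in 47 months, with 70 months in total.
- **The power loss is small.** At the stated 8 a month, power at month 28 is about 78-82%, essentially as planned. The drop to 74-78% appears only if accrual takes the full 24 months. By Schoenfeld, 60/40 with a 40:60 split needs 96 events for 80% power.
- **The source of 115 is not proved.** A reader might infer that only one set of inputs yields 115 events. That is not so: 50/30 with all 170 patients over 24 months also gives 115.0 at month 28. Freedman's formula under 60/40, with 40% in the better group, requires 114 events, and 60/40 with 24-month accrual reaches 114.6 at 36 months. The documents do not settle which inputs were used.
- **The inflation to 170.** A reader might call "Assuming 10% non-evaluable pts we should include a total of 170 pts" an error, since 155/0.9 rounds up to 173 and 170 × 0.9 = 153. But 155 × 1.1 = 170.5; the gap is 2-3 patients and comes from a common convention.
- **Accrual slack.** 155 or 170 patients at 8 a month both fit inside 24 months. This is an unexplained mismatch, and a minor one.

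None of this makes 115 events by month 28 follow from 60/40 with 155 patients.

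**Conclusion.** The event forecast in Protocol 10.2.5 is wrong as written. Under its own 60/40 assumption, 155 patients give about 85-101 events at month 28, and 115 events arrive at about 33-39 months, which is 5-11 months later than stated. The printed 155, 115, 28 months, 8 a month and 80% power fit 50/30 with 40% in the better group, the effect that the SAP states. The SAP then pairs that effect with the 60/40 hazard ratio. The two documents therefore disagree on the design effect, and the SAP disagrees with itself.

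The arithmetic is firm given exponential PFS, uniform accrual, no dropout and N = 155; the ranges cover both accrual readings and both readings of the 40%. That 50/30 was the effect actually used is the likeliest explanation, not an established fact. The consequence is an inconsistent sample-size justification and, at worst, a few points of power if the analysis were done at month 28. It should be corrected, but it does not invalidate the comparison.

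**What to change.** - State which effect assumption produced 155, 115 and 28, and use it in both documents with its matching hazard ratio: 1.74 for 50/30, or 1.79 for 60/40.
- Say whether the 40% in class 0 is the better or the worse group.
- Give one accrual figure: either 8 a month with the 19.4 months (155) or 21.3 months (170) that it implies, or 24 months with the matching monthly rate.
- State in the Protocol that 115 events, not month 28, trigger the PFS analysis, in line with the SAP's use of 115 as the target.
- Restate the expected time to 115 events for N = 155: about 28-33 months under 50/30 or 33-39 months under 60/40, narrowed once accrual and the 40% are fixed.

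The cost is restated figures and possibly a later analysis date. No extra patients are needed.

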In the clinical context, our group retrospectively investigated the role of IGFRp and MMP-7 in metastases or primary CRC in a group of patients with advanced colorectal cancer treated with cetuximab or panitumumab as second or third line treatment (Horndler et al. al., 2009). A total of 104 patients with available tissue from 168 patients were taken to analyze the mutational status of RAS and BRAF and the expression of MMP-7 and IGFRp. There were no significant differences in response rate (18.8% vs. 15%), PFS (3.3 vs. 3 m), and OS (7.76 vs. 7 m) between the total and selected cohorts. Expression of MMP-7 and IGFRp was observed in 49% and 52% of patients, respectively. Co-expression of MMP-7 and IGFRp (double positive group [IGFRp + / MMP-7 +]) was observed in 27/104 patients (26%) and in 15/71 patients (24%) in patients with RAS and BRAF not mutated. There was no correlation between RAS and BRAF mutational status and the double positive group (IGFRp + / MMP-7 +) ($p = 0.52$). In the subgroup of patients with RAS and non-mutated BRAF, the group with double positivity (IGFRp + / MMP-7 +) presented a lower response than patients without double positivity ($p = 0.002$) and showed a trend towards a disappointing PFS of 91 days versus 121 days ($p = 0.09$) and a poor OS of 196 days (95% CI: 175-215) versus 294 days (95% CI: 182-344) ($p = 0.002$).

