Diagnosis and main criteria for inclusion	
Main inclusion criteria:
 
Patients, men or women 18 years or older, with advanced and/or metastatic wt-KRAS and NRAS colorectal cancer, histologically or cytologically confirmed and radiologically measurable, with ECOG performance status 0 to 2 and adequate hepatic, renal, and haematological function, all after provision of the patients' signed informed consent. Patients were included only if their tumour samples were of the required quality to perform the proposed biomarker tests. The centralised review laboratory was responsible for evaluating the quality of the tumour blocks.
 
Main exclusion criteria:
 
Patients who have received a previous systemic treatment for their metastatic colorectal cancer were excluded from the trial. Those who have previously undergone metastatic surgery (liver, lung, or other), presenting with central nervous system metastasis or significant cardiovascular disease will also be excluded.

Test product, dose and mode of administration	Cetuximab (Erbitux® 5 mg/ml - 500 mg/m ² every 2 weeks) was administered intravenously with an infusion pump, gravity drip, or a syringe pump. The duration of the cetuximab infusion was 120 minutes for the first cycle, 90 minutes for the second, and 60 minutes for the third and subsequent cycles. Prior to all cetuximab infusions, patients received adequate premedication as prophylaxis against an acute hypersensitivity reaction with an antihistamine and a corticosteroid, according to local practice.

Duration of treatment	Cetuximab (Erbiflux®) 500 mg/m ² bi-weekly until underlying disease progression.
Criteria for evaluation	
Primary: PFS comparing 2 cohorts of patients, which will be defined according to the classification based on the predictive capacity of each biomarker.
 
Secondary:
 
 • ORR: incidence of a complete or partial response according to the revised RECIST 1.1 criteria. • Duration of response (DoR); calculated only for the subjects who present an objective response and considering the time from the first objective response to radiological disease progression, according to the revised RECIST 1.1 criteria. For responding subjects without disease progression, DoR are censored at the last date of assessable disease evaluation.

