6.5.2. DETERMINATION OF SAMPLE SIZE

It was the aim of the study to identify two groups based on the well-established categories of clinical variables and the proposed biomarkers which are prognostic regarding PFS. The sample size should be sufficient detect a clinically relevant difference in PFS with a log-rank test between the two groups, given the following assumptions:

- The difference in PFS at 12 months between the two groups is at least 20% (i.e. 50% vs 30%) corresponding to a hazard ration of 1.79 assuming an exponential distribution. • Alpha error (two-tailed): 5%
- Beta error: 20%
- Monthly recruitment: 8 patients
- Percentage of patients with classification= 0: 40%

Initially, the number of patients required to be recruited in 24 months was 155 for 115 events to occur. Assuming a 10% proportion of potentially non-assessable patients, a total of 170 patients were needed to be included. After recruiting 157 patients, it was determined that about 70 of these patients had insufficient samples for biomarker analysis preventing their inclusion into the analysis of the primary objective. Therefore, in order to observe the 115 events necessary to evaluate the primary endpoint, the total number of patients was increased up to 221 recruited in 47 months (4–5 patients per month). Finally, the total study duration was 70 months (recruitment + follow-up).

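### The 10% non-evaluable allowance is unsourced and section 6.1 sets no tissue-adequacy criterion; at the sponsor's own tissue yield, 170 patients give about 105 evaluable and 64–72% power, not 155 and 80%

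*Protocol*

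**What the plan says.** Protocol 10.2.5 sizes the trial on a log-rank comparison: "A minimum difference of 20% (60 vs. 40%) in PFS is expected at 12 months between groups", with "Alpha error (bilateral): 5"%, beta 20% and 40% of patients in classification 0. On numbers and timing it states: "The number of patients required is 155 patients to be recruited in 24 months and a total duration of the trial (recruitment + follow-up) of 28" (the unit is the month). The event target is 115. The inflation step is: "Assuming 10% non-evaluable pts we should include a total of 170 pts". The Synopsis repeats the 10% and the 170. Neither place gives a source for the 10%.

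On tissue, the documents say different things:

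- Protocol 6.1 lists non-mutated KRAS but no requirement that the tumour block be adequate for the other markers. Sections 5.1 and 8.1 let a prior KRAS result stand without re-testing.
- Protocol Synopsis and 5.1 place biomarker measurement before enrolment, and the Synopsis has marker status reviewed to confirm eligibility. Section 8.1 requires the block to be sent to the central laboratory at selection. None of these says that an inadequate block excludes the patient.
- SAP Synopsis: "Patients were included only if their tumour samples were of the required quality to perform the proposed biomarker tests".
- SAP 6.5.2: after 157 patients had been recruited, "about 70 of these patients had insufficient samples for biomarker analysis", so they could not enter the primary analysis. The SAP Synopsis says the target was then raised to 240 and that 221 was finally judged enough.

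Protocol 4.4.2 reports the sponsor group's earlier series: "A total of 104 patients with available tissue from 168 patients were taken to analyze the mutational status of RAS and BRAF". SAP 4.2 describes the same series as 168 available tissue samples.

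**The concern.** A patient without BRAF, PI3K-PTEN and DP results cannot be fully placed in the classification that defines the primary comparison. SAP 6.5.1.3 says as much when it excludes patients with missing biomarker data. The allowance for non-evaluable patients is therefore mainly an allowance for tissue failure. The sponsor group's own series had lost 38% at this step, and the first 157 trial patients reportedly lost about 45%.

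If the allowance is too small and nothing in the eligibility list screens for tissue, patients are treated on the protocol who cannot inform its primary objective, and the comparison has fewer events than planned.

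**Working it through.** **1. Reproduce the plan.** With exponential PFS, 60% vs 40% at 12 months gives HR = ln 0.40 / ln 0.60 = 1.794.

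- Freedman, group ratio 60:40 (φ = 1.5): E = (1.960 + 0.842)² (1 + 1.5 × 1.794)² / (1.5 × 0.794²) = 113.1, so 114. This is the form that comes close to the stated 115. Power at 115 events = Φ(√(1.5 × 115) × 0.794 / (1 + 1.5 × 1.794) − 1.960) = 81%.
- Schoenfeld, 40/60 split: E = (1.960 + 0.842)² / (0.24 × (ln 1.794)²) = 95.8, so 96. Power at 115 events = Φ(√(0.24 × 115) × ln 1.794 − 1.960) = 87%.
- Inflation: 155 × 1.10 = 170.5; 155 / 0.90 = 172.2, so 173. The 170 is an ordinary rounding of a 10% uplift, although 170 × 0.90 = 153. The largest loss that still leaves 155 is 1 − 155/170 = 8.8%.

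**2. Yield figures in the documents.**

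- 104/168 = 61.9% (Protocol 4.4.2; retrospective, second- or third-line).
- (157 − 70)/157 = 87/157 = 55.4% (SAP 6.5.2; the 70 is approximate).
- 181/221 = 81.9% (SAP Synopsis, efficacy set, described there by wild-type RAS status).
- 83%, 89% and 93.5%: KRAS or BRAF determination in the two first-line cetuximab trials described in Protocol 4.1. These are updated rates; the original KRAS rates given there are 45% and 69.1%. They concern mutation tests only, not PTEN, MMP-7 or IGF-1R expression.

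**3. What 170 enrolled gives.** Evaluable = 170 × yield. Events = evaluable × 115/155. Power uses the two formulas above with HR 1.794.

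| Yield | Evaluable | Events | Power, Freedman | Power, Schoenfeld |
|---|---|---|---|---|
| 93.5% | 159 | 118 | 82% | 87% |
| 89% | 151 | 112 | 80% | 86% |
| 83% | 141 | 105 | 77% | 83% |
| 81.9% | 139 | 103 | 76% | 83% |
| 61.9% | 105 | 78 | 64% | 72% |
| 55.4% | 94 | 70 | 60% | 67% |

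At the two lowest yields there are fewer evaluable patients than the 115 events required.

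The SAP has a different effect: "The difference in PFS at 12 months between the two groups is at least 20% (i.e. 50% vs 30"%). Its HR is ln 0.30 / ln 0.50 = 1.737; the 1.79 printed there belongs to 60% vs 40%. With 1.737, power is 60–67% at 61.9% yield and 55–62% at 55.4%.

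**4. Enrolment needed for 155 evaluable.** 155/0.819 = 189.3, so 190. 155/0.619 = 250.4, so 251. 155/0.554 = 279.7, so 280.

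**5. Why the 115/155 ratio is used.** Projecting events to month 28 under 60% vs 40%, with uniform accrual over 19.4 or 24 months, gives only about 85–101 events even with all 155 evaluable. That shortfall has nothing to do with tissue. Holding the plan's ratio fixed isolates the tissue effect.

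**The case against.** A reader might infer that 170 patients cannot give 155 evaluable and 80% power. The documents do not support that. At 93.5% determination, 170 gives 159, and at 82–89% the power loss is small or nil, depending on the formula. The 104/168 series is neither the only yield figure in the Protocol nor a close match: it is retrospective and later-line, whereas this trial collects blocks prospectively at selection. What stands is that the higher rates are for mutation tests only, and the primary markers include protein expression.

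A reader might also infer that the trial has no tissue check at all. The Synopsis and section 5.1 place biomarker measurement before enrolment. On that reading, patients without tissue are screen failures and 10% is the residual loss. But the rule is not in 6.1, and about 70 insufficient samples among 157 recruited patients shows that it was not operating as a gate.

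The 55% yield is itself insecure. If the 70 were permanently lost, at most 221 − 70 = 151 could be evaluable. SAP Table 6 nevertheless has BRAF for 161 + 20 = 181 and DP for 158 + 23 = 181, with PI3K-PTEN for 69 + 98 = 167. The documents do not explain this.

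Two further inferences go too far. Power of 58–66%, from projecting to month 28, includes the separate event shortfall in step 5 of the working. And loss of tissue does not by itself show biased selection: Protocol 4.4.2 reports no significant differences in response, PFS or OS between its total and selected cohorts.

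Finally, the SAP did respond, raising the target to 240 and then 221. That answers the number for this trial. It leaves the Protocol at 170 with an unsourced 10%, and the statements on tissue unreconciled.

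**Conclusion.** The point holds as an unsupported assumption combined with conflicting eligibility text; it is not an arithmetic error. At the yield of the sponsor group's own series, 170 gives 105 evaluable and 64–72% power. At the yield reported for the first 157 patients, it gives 94 and 60–67%. The stated 155 evaluable and 80% power are not delivered at either. At 82% yield the power is 76–83%, and at 93.5% the stated design is met.

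These figures assume exponential PFS, a 40/60 split, the plan's ratio of 115 events per 155 patients, a 60% vs 40% difference, and tissue loss unrelated to outcome. The 62% is a projection from another setting, and the 55% is uncertain because of Table 6.

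**What to change.** Choose one of two routes.

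1. **Gate.** Add to Protocol 6.1 that the central laboratory confirms, before inclusion, that the block is adequate for BRAF, PI3K, PTEN, MMP-7 and phosphorylated IGF-1R. Tissue loss then becomes screen failure, and the allowance in 10.2.5 covers only residual loss, which still needs a stated basis.
2. **No gate.** Replace the 10% in 10.2.5 with a sourced rate, and state the evaluable number, events and power that 170 gives across the documented range.

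Do not combine the gate with a 38% allowance, which would count the same loss twice.

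Under either route, reconcile the Protocol Synopsis, 5.1, 6.1 and 8.1 with the SAP Synopsis statement on sample quality and with SAP 6.5.2. A new criterion cannot make the SAP statement true of patients already recruited, so the SAP should say how many lacked each marker and how that fits Table 6. Correct SAP 4.2, which turns 168 patients into 168 available samples.

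The cost is mainly wording. The block is already sent at selection, so the gate adds no new sample, but the adequacy result must be back before inclusion. The downside of the gate is more screen failures (170 / 0.619 = about 275 screened per 170 included at 62% yield) and slower accrual.
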